5.2 Analysis Windows

Definition of Study Days (Days Relative to the First Dose of Study Drug)

Study Days are calculated for each collection date relative to the date of the first dose of study drug. It is defined as the number of days between the date of the first dose of study drug and the collection date. Study days are negative values when the collection date of interest is prior to the first study drug dose date. Study days are positive values when the collection date of interest is on or after the first study drug dose date. The day of the

first dose of study drug is defined as Study Day 1, while the day prior to the first study drug dose is defined as Study Day –1 (there is no Study Day 0). Study days are used to map actual study visits to the protocol-specified study visits.

Definition of Analysis Windows

The following rules will be applied to assign actual subject visits to protocol-specified visits. For each protocol-specified study visit, a target study day will be identified to represent the corresponding visit along with a window around the target day. Windows will be selected in a non-overlapping fashion so that a collection date does not fall into multiple visit windows. If a subject has two or more actual visits in one visit window, the visit closest to the target day will be used for analysis. If two visits are equidistant from the target day, then the later visit will be used for analysis.

The visit window and the target study day for each protocol-specified visit in Period 1 are displayed in [Table 4](#) and [Table 6](#) (depending on the different visit schedules of different endpoints). Visit windows for protocol-specified visits in Period 2 are defined similarly.

Table 4. Analysis Windows for Efficacy Analysis for Period 1 (for ACR Components and Morning Stiffness)

Protocol Specified Visit Week	Lower Bound	Target Day	Upper Bound
Baseline	–99	1 ^a	1
1	2	8	11
2	12	15	22
4	23	29	43
8	44	57	71
12	72	85	min (99, first dose date of Period 2)

a. Day of first dose of study drug.

Table 5. Analysis Windows for Safety Analysis for Period 1 (for Labs and Vital Signs)

Protocol Specified Visit Week	Lower Bound	Target Day	Upper Bound
Baseline	-99	1 ^a	1
2	2	15	22
4	23	29	43
8	44	57	71
12	72	85	min (99, first dose date of Period 2)

a. Day of first dose of study drug.

Table 6. Analysis Windows for Efficacy Analysis for Period 1 (for EQ-5D-5L, SF-36, FACIT-F and RA-WIS)

Protocol Specified Visit Week	Lower Bound	Target Day	Upper Bound

- Patient's assessment of pain within last week (mm on a 100-mm horizontal VAS)
- Patient's global assessment of disease activity within last 24 hours (mm on a 100-mm horizontal VAS)
- Health Assessment Questionnaire Disability Index of the (HAQ – DI) (range: 0 to 3)
- High sensitivity C-reactive protein (hsCRP) (mg/L)
- Erythrocyte sedimentation rate (ESR) (mm/hr)

Other Baseline RA Disease Characteristics

- Anti-cyclic citrullinated peptide (Anti-CCP) (units)
- Anti-CCP status: Positive or Negative
- Rheumatoid Factor (RF) (units)
- Rheumatoid Factor (RF) status: Positive or Negative

- DAS28 [hsCRP]
- DAS28 [ESR]
- DAS28 Categories:
 - DAS28 > 5.1 (High Disease Activity)
 - DAS28 ≤ 5.1
- Clinical Disease Activity Index (CDAI)
- CDAI categories:
 - CDAI > 22 (High Disease Activity)
 - CDAI ≤ 22
- Simplified Disease Activity Index (SDAI)
- SDAI categories:
 - SDAI > 26 (High Disease Activity)
 - SDAI ≤ 26

Patient Report Outcomes at Baseline

- Morning stiffness (severity and duration)
- Functional Assessment of Chronic Illness Therapy-Fatigue (FACIT-F)
- Work Instability Scale for Rheumatoid Arthritis (RA-WIS)
- 36-Item Short Form Health Survey (SF-36) Version 2: physical component summary, mental component summary and the 8 sub-domain scores
- EQ-5D-5L

Clinical Tests at Screening

- Chest x-ray
- ECG
- Tuberculin PPD skin test, QuantiFERON TB Gold test
- Hepatitis Testing
- Serum pregnancy test

Immunization History

- BCG immunization
- Herpes Zoster immunization (regardless of Type of vaccine)
- Hepatitis B immunization

Tobacco/Nicotine and Alcohol Use

- Tobacco/Nicotine Use [user, ex-user, non-user, unknown]
- Alcohol Use [drinker, ex-drinker, non-drinker, unknown]

6.2 Medical History

Medical history data will be summarized and presented for FAS population using body systems and conditions/diagnoses as captured on the CRF. The body systems will be presented in alphabetical order and the conditions/diagnoses will be presented in alphabetical order within each body system. The number and percentage of subjects with a particular condition/diagnosis will be summarized for each randomized treatment group as well as overall. Subjects reporting more than one condition/diagnosis within a body system will be counted only once for that body system. No statistical comparison will be performed for medical history reporting.

6.3 Prior Treatment and Concomitant Medications

Prior and concomitant medications will be summarized by each randomized treatment group as well as overall for FAS. Prior medications are those medications taken prior to the first dose of study drug. This includes medications with a start date before the first study drug administration date, regardless of the end date of these medications. Medications taken on the day of the first dose of study drug are not counted as prior medications. Concomitant medications are those medications, other than study drug, taken after the first dose of study drug and within 1 day of the last dose of study drug. This includes medications with a start date between first study drug administration and last study drug administration + 1 day, as well as, medications with a start date prior to

first dose of study drug and which are ongoing after first dose of study drug. Medications taken on the day of the first dose of study drug are counted as concomitant medications.

The number and percentage of subjects who received a prior medication and the number and percentage of subjects who received a concomitant medication will be tabulated separately by the generic name assigned by the most current version of the World Health Organization (WHO) Drug Dictionary.

6.4 Protocol Deviations

Protocol deviations are categorized as follows based on ICH deviation criteria:

- Those who entered the study even though they did not satisfy the entry criteria
- Those who developed withdrawal criteria during the study and were not withdrawn
- Those who received the wrong treatment or incorrect dose, and
- Those who received an excluded or prohibited concomitant medication.

The protocol deviations listed above will be summarized and listed by treatment group.

7.0 Patient Disposition

The following will be summarized by randomized treatment group as well as overall:

- number of subjects randomized,
- number of subjects included in key analysis populations (Full Analysis Set and Per Protocol Analysis Set for primary efficacy analysis, Safety Analysis Set for Period 1),
- number of subjects who completed Period 1,
- number of subjects who entered Period 2,
- number of subjects on-going in Period 2 (if applicable),
- number of subjects who completed overall study (Period 1 and Period 2) (if applicable).

This summary will be repeated by site.

Prematurely discontinued study drug details will be further summarized separately for Period 1 and Period 2 as follows.

Period 1

The number and percentage of subjects completed Period 1 and prematurely discontinued study drug in Period 1 will be summarized by randomized treatment group, with the primary reasons for discontinuation collected from CRF by the following categories:

- Adverse event (AE)
- Withdrew consent
- Lost to follow-up
- Lack of efficacy
- Other.

Subjects may have more than one reason for discontinuing, but only the primary reason will be summarized.

In addition, the number and percentage of subjects enrolled in Period 2 will also be summarized by randomized treatment group.

Period 2

Period 2 patient dispositions and reason for discontinuation of study drug will be summarized for overall and by actual treatment in Period 2 defined as follows:

1. Upadacitinib (ABT-494) 7.5 mg QD
2. Upadacitinib (ABT-494) 15 mg QD
3. Upadacitinib (ABT-494) 30 mg QD

Among the subjects who entered Period 2, the number and percentage of subjects completed, on-going (if applicable), and prematurely discontinued in Period 2 will be summarized.

For subjects who prematurely discontinued study drug the primary reasons for discontinuation will be summarized by the following categories (as collected in CRF):

- Adverse event (AE)
- Withdrew consent
- Lost to follow-up
- Lack of efficacy
- Other.

Subjects may have more than one reason for discontinuing, but only the primary reason will be summarized.

8.0 Study Drug Exposure and Compliance

The duration of exposure to study drug will be summarized for the safety analysis set by the following groups.

1. Upadacitinib (ABT-494) 7.5 mg QD

This includes Upadacitinib 7.5 mg QD exposure from subjects starting on Upadacitinib 7.5 mg QD and subjects switching from placebo to Upadacitinib 7.5 mg QD.

2. Upadacitinib (ABT-494) 15 mg QD

This includes Upadacitinib 15 mg QD exposure from subjects starting on Upadacitinib 15 mg QD and subjects switching from placebo to Upadacitinib 15 mg QD.

3. Upadacitinib (ABT-494) 30 mg QD

This includes Upadacitinib 30 mg QD exposure from subjects starting on Upadacitinib 30 mg QD and subjects switching from placebo to Upadacitinib 30 mg QD.

4. Placebo

The duration of exposure to study drug will be summarized for each group as specified above, with the number of subjects, mean, standard deviation, median, minimum and maximum values. In addition, the number and percentage of subjects exposed to study drug will be summarized for the following cumulative duration intervals.

- ≥ 1 weeks
- ≥ 2 weeks
- ≥ 1 month
- ≥ 3 months
- ≥ 6 months
- ≥ 9 months
- ≥ 12 months
- ≥ 18 months
- ≥ 2 years
- ≥ 2.5 years
- ≥ 3 years
- ≥ 4 years

8.1 Compliance

Study drug compliance will be summarized for each treatment group for Period 1. The compliance is defined as the number of tablets taken (i.e., the difference between the number of tablets dispensed and the number of tablets returned) during the subject's participation in Period 1 divided by the number of days that the subject was in the Treatment Phase of Period 1.

9.0 Efficacy Analysis

9.1 General Considerations

There are two sets of planned efficacy analysis: efficacy analysis for Period 1 and long-term efficacy analysis. All efficacy analyses will be carried out using the FAS population.

9.1.1 Efficacy Analysis at Different Phases of the Study

Efficacy Analysis for Period 1

Standard efficacy analysis by randomized treatment groups (Upadacitinib 7.5 mg QD, Upadacitinib 15 mg QD, Upadacitinib 30 mg QD and the combined placebo groups) will be performed on efficacy data for Period 1 (up to Week 12). No protocol-defined treatment switching will occur prior to the time point. Formal statistical inference will be generated, and results from this set of analysis will be used as the key efficacy findings of this study.

Long Term Efficacy Analysis

Long term efficacy analysis will be performed on As Observed data (defined in Section 9.1.2) by randomized treatment group sequence as described below:

1. Upadacitinib (ABT-494) 7.5 mg QD
2. Upadacitinib (ABT-494) 15 mg QD
3. Upadacitinib (ABT-494) 30 mg QD
4. Placebo → Upadacitinib (ABT-494) 7.5 mg QD
5. Placebo → Upadacitinib (ABT-494) 15 mg QD
6. Placebo → Upadacitinib (ABT-494) 30 mg QD.

There will be no statistical testing; only descriptive statistics and confidence intervals will be provided.

9.1.2 Definition of Missing Data Imputation

Non-Responder Imputation (NRI) Approach

The NRI approach will categorize any subject who has missing value for categorical variables at a specific visit as non-responder for that visit. In addition, subjects who prematurely discontinue from study drug will be considered as non-responders for all subsequent visits after discontinuation.

Observed Cases (OC)

The OC analysis will not impute values for missing evaluations, and thus a subject who does not have an evaluation on a scheduled visit will be excluded from the OC analysis for that visit. In addition, the OC will not use values after premature discontinuation of study drug. This sensitivity analysis will only be applied to the analysis in Period 1.

As Observed (AO)

The AO analysis will not impute values for missing evaluations, and thus a subject who does not have an evaluation on a scheduled visit will be excluded from the AO analysis for that visit. Regardless of treatment switching or premature discontinuation of study drug, all observed data will be used in the analysis. The AO analysis will be applied to long term efficacy analysis.

Mixed Effect Model Repeat Measurement (MMRM)

The repeated measure analysis will be conducted using mixed model including observed measurements at all visits. The mixed model includes the categorical fixed effects of treatment, visit and treatment-by-visit interaction, main stratification factors at randomization, and the continuous fixed covariates of baseline measurement. An unstructured variance covariance matrix will be used. The parameter estimations is based on assumption of data being missing at random and using the method of restrictive maximum likelihood (REML).

Multiple Imputation (MI)

The MI analysis will impute missing data multiple times under appropriate random variation and thus generate multiple imputed "pseudo-complete" datasets. Results will be aggregated across the multiple imputed datasets, overcoming drawbacks of the single imputation methods.

9.2 Efficacy Analysis for Period 1

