9.2.3 Key Secondary Efficacy Analyses

Key secondary endpoints at Week 12 are:

1. Change from baseline in DAS28 (CRP);
2. Change from baseline in HAQ-DI;
3. ACR50 response rate;
4. ACR70 response rate;
5. Change from baseline in Short Form-36 (SF-36) Physical Component Score (PCS);
6. Proportion of subjects achieving LDA based on DAS28 (CRP);
7. Proportion of subjects achieving Clinical remission (CR) based on DAS28 (CRP);
8. ACR20 response rate of Week 1;
9. Change from baseline in Functional Assessment of Chronic Illness Therapy-Fatigue (FACIT-F);
10. Change from baseline in Work Instability Scale for Rheumatoid Arthritis (RA-WIS);
11. Change from baseline in morning stiffness (severity).

For binary endpoints, frequencies and percentages will be reported for each randomized treatment group. Similar analyses as for the primary endpoint will be conducted.

For the major RA continuous endpoints DAS28 and HAQ-DI change from baseline, statistical inference will be conducted using analysis of covariance (ANCOVA) coupled

with MI for missing data handling. Specifically, the ANCOVA model will include treatment as the fixed factor, and the corresponding baseline value and the stratification factor prior bDMARD use (Yes/No) as the covariates. For other continuous endpoints, statistical inference will be conducted using the MMRM model as described in Section 9.1.2, with the main stratification factor being prior bDMARD use (Yes/No). From both the MI and MMRM analyses, the LS mean and 95% CI will be reported for each randomized treatment group; the LS mean treatment difference and associated 95% CI and p-value will be reported comparing each Upadacitinib dose group with the combined placebo group.

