Binary Endpoints: 
 ACR50/70 response at Week 12 ACR20 response at Week 1 Proportion of subjects achieving LDA based on DAS28 (CRP) at Week 12 Proportion of subjects achieving Clinical remission (CR) based on DAS28 (CRP) at Week 12 	
 Point estimate and 95% CI of the response rate for each treatment group. The 95% CI will be based on normal approximation. Point estimate, 95% CI and p-value for the treatment comparison between each Upadacitinib dose group and the combined placebo group using the Cochran-Mantel-Haenszel test adjusting for stratification factor prior bDMARD use. The 95% CI will be based on normal approximation. Imputation: NRI for primary analysis and OC for sensitivity analysis Analysis Set: FAS

Table 9. Summary of Efficacy Variables and Corresponding Analyses for Efficacy Analysis in Period 1 (Continued)

Efficacy Variables	Analysis Method
Key Secondary Variables (continued)	
Continuous Endpoints: 
 Change from baseline in DAS28 (CRP) at Week 12 Change from baseline in HAQ-DI at Week 12 Change from baseline in SF-36 Physical Component Score (PCS) at Week 12 Change from baseline in FACIT-F Change from baseline in RA-WIS Change from baseline in morning stiffness (severity). 	
 LS mean, and 95% CI within each treatment group and LS mean, 95% CI and p-values between each Upadacitinib dose group and the combined placebo group using ANCOVA model with treatment, prior bDMARD use and baseline value as covariates. Imputation: MI Analysis Set: FAS LS mean and 95% CI within each treatment group and LS mean, 95% CI and p-values between each Upadacitinib dose group and the combined placebo group using MMRM model with fixed effects of treatment, visit and treatment-by-visit interaction, prior bDMARD use and baseline value as covariate. Analysis Set: FAS
Additional Variables (Summarized at all Visits up to Week 12)	

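### The SAP's MMRM uses one baseline slope for all visits; a baseline-by-visit term costs almost nothing and may improve Week 12 precision for four key secondary endpoints

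*SAP*

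**What the plan says.** SAP 9.1.2 defines the MMRM with treatment, visit, treatment-by-visit, and the "main stratification factors at randomization, and the continuous fixed covariates of baseline measurement". It adds: "An unstructured variance covariance matrix will be used". SAP 9.2.4 and Table 9 (SAP 9.2.7) repeat the specification: "using MMRM model with fixed effects of treatment, visit and treatment-by-visit interaction, prior bDMARD use and baseline value as covariate". The only interaction with visit is treatment-by-visit.

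SAP 9.2.3 divides the six continuous key secondary endpoints. It states "For the major RA continuous endpoints DAS28 and HAQ-DI change from baseline, statistical inference will be conducted using analysis of covariance (ANCOVA) coupled" with multiple imputation. It then states: "For other continuous endpoints, statistical inference will be conducted using the MMRM model as described in Section 9.1.2". The second sentence covers SF-36 PCS, FACIT-F, RA-WIS and morning stiffness severity.

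SAP Table 4 gives morning stiffness five post-baseline windows (Weeks 1, 2, 4, 8, 12). SAP Table 6 gives the other three endpoints two (Weeks 4 and 12).

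The protocol differs. Section 8.1.4.1.2 names ANCOVA for all continuous key secondary endpoints, and Section 8.1.4.1.5 makes multiple imputation the primary approach for them. The protocol synopsis is dated 23 February 2018; the SAP is Version 1.0, 31 August 2017.

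**The concern.** The model lets the treatment effect and the covariance change freely from visit to visit, yet fixes the relation between baseline and change. If that relation shifts between Week 1 and Week 12, the fitted slope is a compromise across visits. The Week 12 comparison is then adjusted with the wrong slope, and part of any chance baseline difference between arms of 48 stays in the contrast.

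What is at stake is precision at Week 12 for four key secondary endpoints. There is also an internal mismatch. Change in DAS28 (CRP) and in the ACR components, which include HAQ-DI, is analysed by ANCOVA under SAP 9.2.3 and again by this MMRM under SAP 9.2.4. The same Week 12 contrast is therefore reported with two different baseline adjustments.

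**Working it through.** **Inputs.** Model terms come from SAP 9.1.2, 9.2.4 and Table 9, and visit schedules from SAP Tables 4 and 6. There are 48 subjects per arm with the placebo groups pooled, and 5% dropout (Protocol 8.2, SAP 4.3). The documents state no SD, correlation, standard error or power for these four endpoints, so there is no plan figure to reproduce, and every correlation below is an assumption.

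**Formula.** Let b_j be the slope of the visit-j score on baseline in baseline-SD units. The slope for change is b_j − 1, so differences between visits are the same. Let Σ be the residual covariance given baseline. The common slope is

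b* = (1ᵀΣ⁻¹b) / (1ᵀΣ⁻¹1).

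The Week 12 standard error as written, relative to that with a baseline-by-visit term, is

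√[1 + Var(baseline) × (b₁₂ − b*)² / σ₁₂²].

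**Worked case, two visits, moderate decay.** Take SD 1 at every visit and correlation 0.3 + 0.4 × 2^(−t/4) at a lag of t weeks.
- Slopes: b₄ = 0.50, b₁₂ = 0.35. The Week 4 to Week 12 correlation (lag 8) is 0.40.
- Residual variances: 1 − 0.50² = 0.75 and 1 − 0.35² = 0.8775. Residual covariance: 0.40 − 0.50 × 0.35 = 0.225.
- Weights: Week 4 ∝ 0.8775 − 0.225 = 0.6525; Week 12 ∝ 0.75 − 0.225 = 0.525.
- b* = (0.6525 × 0.50 + 0.525 × 0.35) / 1.1775 = 0.433.
- Ratio: √(1 + 0.083² / 0.8775) = 1.004.

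**Range of assumed patterns (SD constant).** The formula columns give as written ÷ with the term. The simulation columns give the model standard error with the term ÷ as written, from REML fits to 450 simulated trials per row (4 × 48 subjects, 5% dropout).

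| Pattern | Baseline correlation, Week 1 → 12 | Formula, 5 visits | Formula, 2 visits | Simulation, 5 visits | Simulation, 2 visits |
|---|---|---|---|---|---|
| Equal slopes | 0.50 → 0.50 | 1.000 | 1.000 | 1.002 | 1.001 |
| Early fall, then plateau | 0.50 → 0.30 | 1.003 | 1.000 | – | – |
| Moderate decay | 0.64 → 0.35 | 1.016 | 1.004 | 0.986 | 0.997 |
| Stronger decay | 0.70 → 0.28 | 1.039 | 1.009 | 0.965 | 0.991 |
| Continuous autoregressive | 0.90 → 0.30 | 1.140 | 1.035 | 0.879 | 0.966 |

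Check of the largest entry: b* = 0.82, b₁₂ = 0.30, residual variance 1 − 0.30² = 0.91, so √(1 + 0.52² / 0.91) = 1.139, which agrees with 1.140 apart from rounding. The empirical standard errors in the simulations gave ratios of 0.995, 0.970 and 0.873 (five visits) and 0.996, 0.986 and 0.977 (two visits) for the last three rows.

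The SD pattern also matters. With SD rising over visits, the autoregressive figures drop to 1.085 and 1.026, while constant correlation gives 1.003 and 1.001.

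**Cost of the term.** With K visits it adds K − 1 parameters: 4 for morning stiffness, 1 for each of the others. With equal slopes the standard error rises by 0.1–0.2%.

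**The case against.** The strongest objection is that the gain is conditional and its conditions appear nowhere in the documents. That stands. If the Week 12 slope equals the pooled slope, the term gains nothing and costs about 0.1–0.2% of the standard error. Nor do the documents show that early visits are less variable and so dominate the pooled slope. With SD 1.0 at Week 4, 0.9 at Week 12 and correlation 0.8, the Week 12 weight is (1 − 0.72) / [(1 − 0.72) + (0.81 − 0.72)] = 0.28 / 0.37 = 76%.

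A reader might infer three stronger claims that the documents do not support.
- **That morning stiffness must gain most because it has five visits.** This holds only if the endpoints share a correlation pattern. With residual SD 0.9 and equal residual correlations, stiffness slopes of −0.25, −0.40, −0.45, −0.45, −0.45 average −0.40, and the loss is √(1 + 0.05² / 0.81) − 1 = 0.15%. A two-visit endpoint moving from −0.25 to −0.50 averages −0.375 and loses √(1 + 0.125² / 0.81) − 1 = 1.0%. The ranking reverses.
- **That the restriction wastes about 7% of the subjects.** That matches the five-visit stronger-decay row (1 − 1/1.039² = 7.4%). It is above anything found for the three two-visit endpoints, where 1.035 gives 6.6% in the extreme row and 1.009 gives 1.8% in the row above it.
- **That leftover baseline imbalance is a bias on top of the lost precision.** Under randomization they are the same effect, and it should be counted once.

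A further objection is that following the protocol's ANCOVA would make the point moot for these four endpoints, since a Week 12 ANCOVA has its own slope. This is right about the order of work: the choice of primary method should be settled first. It does not rescue the MMRM as the SAP now writes it, which SAP 9.2.4 also applies to the additional continuous endpoints.

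**Conclusion.** The point holds as a low-cost improvement. The single baseline slope is plain in the text and affects exactly four key secondary endpoints. Under the assumed patterns, the Week 12 standard error as written is larger by 0% to about 14% with five visits and by 0% to 3.5% with two. For the two-visit endpoints about 1% or less is the more likely figure, since only the autoregressive patterns exceeded 0.9% in the range tried. These sizes rest wholly on assumed correlations and SDs.

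It would go too far to say that the term is certain to lower the standard error, or that the model as written gives invalid comparisons. The pairwise comparisons are nominal (Protocol synopsis), and multiplicity control covers only the ACR20 trend test (SAP 9.2.5). The primary conclusion does not change.

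**What to change.** 1. State which analysis is primary for SF-36 PCS, FACIT-F, RA-WIS and morning stiffness severity: the protocol's ANCOVA with multiple imputation (8.1.4.1.2, 8.1.4.1.5) or the SAP's MMRM (9.2.3). Align the two documents.
2. Wherever the MMRM is kept, add the baseline-by-visit interaction in SAP 9.1.2, 9.2.3, 9.2.4 and Table 9.

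The cost is one model term, using data already collected: 4 parameters with five visits, 1 with two, and about 0.1–0.2% of the standard error if the slopes are equal. It should be specified before unblinding; Protocol 8.1 requires the SAP to be final before the Week 12 database lock. If that point has passed, report the extended model as a labelled sensitivity analysis.
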